5.7 Follow-Up After Subject Discontinuation of Study Drug or from Study

For subjects who

[figure not shown]
- are ineligible for retreatment because of not meeting GL severity criterion on Day 43, the
 subjects will be followed weekly per the visit schedule (Appendix D) until the FWS grades
 assessed by both investigator and subject have returned to moderate or severe (investigator
 and subject grades do not need to match) before being discontinued by completing either the
 Early Exit or Study Exit Visit.
- are ineligible for retreatment because of pregnancy, the subjects will not receive study drug.
 They can either be discontinued from the study after Early Exit Visit procedures are completed or remain in the study for all safety follow-up assessments.
- prematurely discontinue study treatment, or who prematurely discontinue study participation (due to withdrawal of informed consent or if the protocol-specified discontinuation criteria are met), the procedures outlined for the Early Exit visit (in Appendix D) should be completed as soon as possible, preferably within 2 weeks, but no sooner than 30 days since last treatment.

5.8 Study Drug

All subjects will receive AGN-151586 or matching placebo, which will be prepared at the investigator site as an injectable solution and administered on Baseline Day 1. Based on meeting the retreatment

criteria, the subject may be retreated at Day 43. See Operations Manual (Section 3.15) for information about study drug administration.

drug will only be used for the conduct of this study.

Detailed study drug preparation instructions will be provided to sites in the Pharmacy Manual.

Table 3. Identity of Investigational Medicinal Product

Investigational Medicinal Product	AGN-151586	Placebo for AGN-151586

5.9 Randomization/Drug Assignment

At the Screening Visit, all subjects will be assigned a unique identification number using the IRT. For subjects who rescreen, the screening number assigned by the IRT at the initial Screening Visit should be used. The IRT will assign a randomization number that will encode the subject's treatment group assignment according to the randomization schedule (3:1 ratio AGN-151586:placebo).

Randomization will be stratified by investigator site, toxin use history (for aesthetic purpose), and baseline GL severity at maximum frown.

To support this, the site will manually enter the subject's Baseline Day 1 FWS score (moderate or severe; per eligibility criteria, the investigator and subject FWS assessments must be identical), toxin use history (for aesthetic purpose), and the Baseline Day 1 FLO-11 total score (as calculated by the electronic data capture [EDC] after the subject completes the questionnaire) in to the IRT.

All AbbVie personnel with direct oversight of the conduct and management of the trial (with the exception of AbbVie Drug Supply Management Team), the investigator, study site personnel, and the subject will remain blinded to each subject's treatment throughout the study. To maintain the blind, the

AGN-151586 / matching placebo provided for the study will be identical in appearance. The IRT will provide access to unblinded subject treatment information in the case of a medical emergency.

5.10 Protocol Deviations

AbbVie does not allow intentional/prospective deviations from the protocol except when necessary to eliminate an immediate hazard to study subjects. The investigator is responsible for complying with all protocol requirements, written instructions, and applicable laws regarding protocol deviations. If a protocol deviation occurs (or is identified, including those that may be due to the COVID-19 pandemic), the investigator is responsible for notifying IEC/IRB, regulatory authorities (as applicable), and AbbVie.

5.11 Data Monitoring Committee

A data monitoring committee is not planned for this study.

6 SAFETY CONSIDERATIONS

6.1 Complaints and Adverse Events

Complaints

A complaint is any written, electronic, or oral communication that alleges deficiencies related to the physical characteristics, identity, quality, purity, potency, durability, reliability, safety, effectiveness, or performance of a product/device. Complaints associated with any component of this investigational product must be reported to AbbVie.

Product Complaint

A product complaint is any complaint related to the biologic or drug component of the product or to the medical device component(s).

For a product this may include, but is not limited to, damaged/broken product or packaging, product appearance whose color/markings do not match the labeling, labeling discrepancies/inadequacies in the labeling/instructions (e.g., printing illegible), missing components/product, device damage or not working properly, or packaging issues.

Product complaints concerning the investigational product and/or device must be reported to AbbVie within 24 hours of the study site's knowledge of the event.

Reporting will be done via EDC. The date the product complaint details are entered into EDC and the form is saved represents the date reported to AbbVie. A back-up paper form will be provided for reporting complaints related to unassigned product or in the event of an EDC system issue. If a back-up paper form is used, the date the form is emailed to [contact] represents the date reported to AbbVie.

All follow-up information is to be reported to the sponsor (or an authorized representative) and documented in source as required by the sponsor. Product complaints associated with AEs will be reported in the study summary. All other complaints will be monitored on an ongoing basis. Product complaints occurring during the study will be followed up to a satisfactory conclusion.

Medical Complaints/Adverse Events and Serious Adverse Events

An AE is defined as any untoward medical occurrence in a subject or clinical investigation subject administered a pharmaceutical product and which does not necessarily have a causal relationship with this treatment. An AE can therefore be any unfavorable and unintended sign (including an abnormal laboratory finding or vital sign measurement), symptom, or disease temporally associated with the use of a medicinal (investigational) product, whether or not the event is considered causally related to the use of the product.

Such an event can result from use of the drug as stipulated in the protocol or labeling, as well as from "special situations" such as accidental or intentional overdose, medication error, occupational or accidental exposure, off-label use, drug abuse, drug misuse, or drug withdrawal, all which must be reported whether associated with an AE or not. Any worsening of a pre-existing condition or illness is considered an AE. Worsening in severity of a reported AE should be reported as a new AE. Laboratory abnormalities and changes in vital signs are considered to be AEs only if they result in discontinuation from the study, necessitate therapeutic medical intervention, and/or if the investigator considers them to be AEs.

The investigators will monitor each subject for clinical and laboratory evidence of AEs on a routine basis throughout the study. All AEs will be followed to a satisfactory conclusion.

An elective surgery/procedure scheduled to occur during a study will not be considered an AE if the surgery/procedure is being performed for a pre-existing condition and/or the surgery/procedure has been pre-planned prior to study entry. However, if the pre-existing condition deteriorates unexpectedly during the study (e.g., surgery performed earlier than planned), then the deterioration of the condition for which the elective surgery/procedure is being done will be considered an AE.

If an AE, whether associated with study drug or not, meets any of the following criteria, it is to be reported to AbbVie clinical pharmacovigilance as a serious adverse event (SAE) immediately without undue delay, but no later than 24 hours, from when the site is made aware of the SAE (refer to Section 4.2 of the Operations Manual for reporting details and contact information):

Death of Subject	An event that results in the death of a subject.
Life-Threatening	An event that, in the opinion of the investigator, would have resulted in immediate fatality if medical intervention had not been taken. This does not include an event that would have been fatal if it had occurred in a more severe form.
Hospitalization or Prolongation of Hospitalization	An event that results in an admission to the hospital for any length of time or prolongs the subject's hospital stay. This does not include an emergency room visit or admission to an outpatient facility.

Congenital Anomaly An anomaly detected at or after birth, or any anomaly that results in

fetal loss.

Persistent or Significant Disability/Incapacity

An event that results in a condition that substantially interferes with the activities of daily living of a study subject. Disability is not intended to include experiences of relatively minor medical significance such as headache, nausea, vomiting, diarrhea, influenza,

and accidental trauma (e.g., sprained ankle).

Important Medical Event
Requiring Medical or Surgical
Intervention to Prevent
Serious Outcome

An important medical event that may not be immediately life-threatening or result in death or hospitalization, but based on medical judgment may jeopardize the subject and may require medical or surgical intervention to prevent any of the outcomes listed above (i.e., death of subject, life-threatening, hospitalization, prolongation of hospitalization, congenital anomaly, or persistent or significant disability/incapacity). Additionally, any elective or spontaneous abortion or stillbirth is considered an important

medical event.

All AEs reported from the time of study drug administration will be collected for at least 30 days after last dose or until the last follow-up visit, whichever is longer, whether solicited or spontaneously reported by the subject. In addition, study procedure-related serious and nonserious AEs will be collected from the time the subject signs the study-specific informed consent.

The following definitions will be used for Serious Adverse Reactions (SAR) and Suspected Unexpected Serious Adverse Reaction (SUSAR):

SAR Defined as all noxious and unintended responses to an Investigational Medicinal

Product (IMP) related to any dose administered that result in an SAE as defined

above.

SUSAR Refers to individual SAE case reports from clinical trials where a causal

relationship between the SAE and the IMP was suspected by either the sponsor or the investigator, is unexpected (not listed in the applicable Reference Safety

Information), and meets one of the above serious criteria.

AbbVie will be responsible for SUSAR reporting for the investigational medicinal product (IMP) in accordance with global and local requirements.

Adverse events will be monitored throughout the study to identify any of special interest that may indicate a trend or risk to subjects.

Adverse Events of Special Interest

There are no AEs of special interest in this study.

Adverse Event Severity and Relationship to Study Drug

The investigators will rate the severity of each AE as mild, moderate, or severe.

The investigator will use the following definitions to rate the severity of each AE:

Mild The AE is transient and easily tolerated by the subject.

Moderate The AE causes the subject discomfort and interrupts the subject's usual

activities.

Severe The AE causes considerable interference with the subject's usual activities

and may be incapacitating or life-threatening.

The investigator will use the following definitions to assess the relationship of the AE to the use of study drug and to the injection procedure:

ReasonableAfter consideration of factors including timing of the event, biologic **Possibility**plausibility, clinical judgment, and potential alternative causes, there is

sufficient evidence (information) to suggest a causal relationship.

No Reasonable After consideration of factors including timing of the event, biologic Possibility plausibility, clinical judgment, and potential alternative causes, there is

insufficient evidence (information) to suggest a causal relationship.

Pregnancy

While not an AE, pregnancy in a study subject must be reported to AbbVie within 24 hours after the site becomes aware of the pregnancy. Subjects who become pregnant can either be discontinued from the study after Early Exit Visit procedures or remain in the study for follow-up through study exit but will receive no further treatment with the study drug. If a pregnancy occurs in a study subject, information regarding the pregnancy and the outcome will be collected. Partner pregnancy information will not be collected.

The pregnancy outcome of an elective or spontaneous abortion, stillbirth or congenital anomaly is considered an SAE and must be reported to AbbVie immediately without undue delay, but no later than 24 hours, from when the site is made aware of the event.

6.2 Other Safety Data Collection

Possible Distant Spread of Toxin

Possible distant spread of toxin (PDSOT) is defined as a possible pharmacologic effect of botulinum toxin at sites noncontiguous and distant from the site of injection. Utilizing a standardized methodology to assess for PDSOT, Medical Dictionary for Regulatory Activities (MedDRA) preferred terms (PTs) that may be associated with botulinum toxin effects have been prospectively identified (the statistical analysis plan [SAP] will include a complete list of these PTs). Adverse events reporting any of these terms will be

medically reviewed on a regular basis throughout the duration of the study and will be summarized in the study clinical study report (CSR).

7 STATISTICAL METHODS & DETERMINATION OF SAMPLE SIZE

7.1 Statistical and Analytical Plans

The statistical methods provided in this protocol will be focused on primary and secondary analyses. Complete and specific details of the statistical analysis will be described in the SAP.

The primary analysis will be conducted after all subjects have completed their end of study visit for the purpose of submission.

7.2 Definition for Analysis Populations

The following population sets will be used for the analyses.

The ITT Population includes all randomized subjects. For double-blind period analyses, subjects will be included in the analysis according to the treatment groups to which they were randomized. For openlabel period analyses, data will be analyzed according to the treatments randomized in the double-blind period and received in the open-label period (i.e., AGN-151586/AGN-151586, AGN-151586/None, Placebo/AGN-151586, Placebo/None).

Baseline analyses and efficacy analyses for US FDA and EU Regulatory agencies will be performed on the ITT population, consisting of all randomized subjects. Subjects will be included in the double-blind period analysis according to the treatment groups to which they were randomized. For open-label period analyses, data will be analyzed according to the treatments randomized in the double-blind period and received in the open-label period (i.e., AGN-151586/AGN-151586, AGN-151586/None, Placebo/AGN-151586, Placebo/None).

Additionally, for EU regulatory agencies only, subgroup analyses will be performed on the ITT population, that also has a baseline FLO-11 total score \leq 50. Analyses will consist of the EU primary and key secondary endpoints.

The Safety Analysis Set consists of all subjects who were treated with at least 1 dose of study drug (i.e., AGN-151586 or placebo). All safety analyses will be performed with subjects analyzed by their actual treatment received in double-blind period/open-label period (i.e., AGN-151586/AGN-151586, AGN-151586/None, Placebo/AGN-151586, Placebo/None), and will be presented with overall safety data for the study (i.e., either period), for double-blind period, and for open-label period. The Safety Analysis Set will be used for all safety analyses.

7.3 Handling Potential Intercurrent Events for the Primary and Key Secondary Endpoints

The primary efficacy endpoint of the composite endpoints for the US FDA and the coprimary endpoints for the EU regulatory agencies (defined in Section 3.2), respectively, will be analyzed based on the ITT population and the following methods will be used to address potential intercurrent events:

- Subjects who did not receive any dose of study drug but are randomized will still be included in the ITT population. For the EU, those who also had baseline FLO-11 total score of ≤ 50 will be included in subgroup analyses of the coprimary and key secondary endpoints.
- Subjects who are randomized but prematurely discontinued the study before assessment of the primary endpoints will be considered as part of the ITT population.
- Subjects who die before assessment of the primary endpoints will count as though they hypothetically continued in the study.
- Subjects who are lost to follow-up and are missing data for the primary endpoints will count as though they hypothetically continued in the study.
- Subjects who are missing assessments or data due to the COVID-19 pandemic and are missing data for the primary endpoints will count as though they hypothetically continued in the study.
- Subjects who are missing data for any other reason for the primary endpoints will count as though they hypothetically continued in the study.

The efficacy analysis of secondary endpoints (defined in Section 3.3) will be analyzed based on the same populations as above with similar methods for addressing potential intercurrent events.

7.4 Statistical Analyses for Efficacy

Demographics, baseline or disease characteristics, medical history, and prior and concomitant medications will be summarized for the ITT population. Medical history data will be reported and summarized separately from prior procedures data for the ITT population. Medical history data and prior procedure data will be coded using the MedDRA. Prior and concurrent procedures will be summarized by MedDRA high level term and PT.

Summary and Analysis of the Primary Endpoints

Analysis of the respective primary endpoints will be conducted on the ITT Population for the US and for the EU regulatory agencies based on treatment as randomized.

The assessments of the severity of GL at maximum frown using the validated FWS is based on the following scale:

- 0 = None
- 1 = Mild
- 2 = Moderate

3 = Severe

The composite primary endpoint for FDA is the following:

• ≥ 2-grade improvement from baseline on the FWS according to both **investigator and subject** assessments of GL severity at maximum frown at Day 7

The coprimary endpoints for EU regulatory agencies consist of the following:

- ≥ 2-grade improvement from baseline on the FWS according to **subject assessment** of GL severity at maximum frown at Day 7, and
- ≥ 2-grade improvement from baseline on the FWS according to **investigator assessment** of GL severity at maximum frown at Day 7.

The attributes of the estimands corresponding to the primary efficacy endpoints for the US FDA and EU regulatory agencies are summarized in Section 3.1.

US FDA: The composite primary responder endpoint for at least a 2-grade improvement will be analyzed using the Cochran-Mantel-Haenszel (CMH) method

The primary endpoint must meet $p \le 0.05$ to be considered successful.

European Union regulatory agencies: The coprimary responder endpoints for ≥ 2 -grade improvement from baseline in the FWS will be analyzed separately using the CMH method

Both coprimary endpoints must meet $p \le 0.05$ to be considered successful.

The evaluation of the equality of the proportions of responders for the primary endpoints at Day 7 will be based on the CMH test stratified by investigator site, toxin use history, and baseline FWS. (Sites may be pooled for stratification purposes if there are too few subjects in a site.) A p-value ≤ 0.05 (2-sided testing) will be claimed as statistically significant.

For primary and secondary endpoints, missing data will first be imputed at the visit level using multiple imputation, and then the responder definitions will be applied. Details are provided in the SAP for missing data handling.

Sensitivity analyses of the primary efficacy variables will be performed to establish their consistency and robustness as well as to further characterize the extent of subjects' responses. As-observed data analysis, as well as missing as non-responder (using non-responder imputation [NRI]) analysis, stratified by baseline FWS and by investigator site are planned for sensitivity analyses.

Secondary efficacy endpoints for the US FDA and EU regulatory agencies are listed in Section 3.3, and include other response definitions for the FWS by investigator and subject, as well as for the FLO-11, FLSQ, and GAC-GL.

The attributes of the estimands corresponding to the secondary efficacy endpoints are summarized in Section 3.1. Analysis of the secondary endpoints will be conducted on the ITT population based on treatment as randomized for the US FDA and the EU regulatory agencies.

For the secondary endpoints, the proportion of responders will be analyzed using the CMH test

. The continuous variables will be analyzed using analysis of covariance with treatment as the main effect,

.

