9.2 Handling of Missing Data

Missing data will be imputed for the DB Period only using the following methods for the efficacy analyses:

- Multiple Imputation: The Multiple Imputation approach will be used as a primary analysis for the primary endpoint, as well as for all secondary endpoints.

- Non-responder Imputation (NRI): The NRI analysis will categorize any subject who does not have evaluation during a specific visit window as a non-responder for that visit. The NRI will be one of the sensitivity analysis approaches in the analyses of categorical variables for the primary efficacy endpoints.
- As Observed (AO): The AO analysis will not impute values for missing evaluations, and thus a subject who does not have an evaluation on a scheduled visit will be excluded from the AO analysis for that visit. AO will include all values collected in the study and will be used for sensitivity analyses for the primary efficacy endpoints.

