9.3.3 Sensitivity and Supplementary Analyses of the Primary Efficacy Endpoints

Sensitivity analyses of the primary efficacy variables will be performed to establish their consistency and robustness as well as to further characterize the extent of subjects'

responses. As-observed data analysis, as well as missing as non-responder (using NRI) analysis, [REDACTED] for sensitivity analyses.

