9.6 Efficacy Subgroup Analyses

For the primary and key secondary endpoints, analyses will be conducted using the following subgroups and descriptive summary statistics provided:

Analyses will be conducted using the following subgroups:

- Sex (Female, Male)
- Age group (<65, \geq 65 years)
- Race (White, non-White)
- Ethnicity (Hispanic or Latino, not Hispanic or Latino)
- Region (North America, EU)

- Baseline FWS at maximum frown (moderate, severe)
- Baseline FLO-11 total score (transformed) \leq 50
- Fitzpatrick skin type (Types I & II, Types III & IV, Types V & VI)

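### In the protocol, the as-observed and non-responder sensitivity tests omit toxin use history from the strata, so comparing them with the main test mixes a change of strata with a change of missing-data rule

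*Protocol*

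**What the plan says.** Protocol 5.9 sets the randomisation factors: "Randomization will be stratified by investigator site, toxin use history (for aesthetic purpose), and baseline GL severity at maximum frown". Protocol 7.4 carries the same three into the main analysis of the primary endpoints, a "CMH test stratified by investigator site, toxin use history, and baseline FWS", and lets sparse sites be pooled. For the primary and secondary endpoints, "missing data will first be imputed at the visit level using multiple imputation", and the responder definition is applied afterwards.

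The same section then plans as-observed and NRI analyses of the primary endpoints, "stratified by baseline FWS and by investigator site are planned for sensitivity analyses". Toxin use history is not mentioned.

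SAP 9.2 defines the two analyses only by what they do with missing evaluations. On NRI: "The NRI will be one of the sensitivity analysis approaches in the analyses of categorical variables for the primary efficacy endpoints". On as-observed: "The AO analysis will not impute values for missing evaluations". The place in SAP 9.3.3 where strata would be named is blacked out ("analysis, [REDACTED] for sensitivity analyses"), and so is the corresponding wording for the main test in SAP 9.3.2.

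**The concern.** SAP 9.2 distinguishes multiple imputation, NRI and as-observed purely by their missing-data rule. A reader will therefore take any difference between the main p-value and a sensitivity p-value as the effect of that rule. As the protocol is worded, the strata differ too. Agreement may come partly from coarser strata recovering precision, and disagreement may be softened in the same way.

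No visible text plans a multiple-imputation test on the reduced strata, which would separate the two changes. These are also the only two sensitivity analyses named for the primary endpoints. What is at stake is how the robustness evidence is read, not the validity of the primary test.

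**Working it through.** **Inputs from the documents.** About 600 subjects at 3:1, so 450 and 150 (SAP 2.4); approximately 38 sites (Protocol synopsis); two-sided 0.05; the strata quoted above.

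**Assumptions, not in the documents.** Block size, prevalence of prior toxin use, spread of site sizes, pooling threshold, response rates, amount of missing data and prognostic effects.

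**1. The plan's own figure.** SAP 2.4 states power above 99%, but the assumed rates are blacked out, so it cannot be reproduced directly. With the pooled chi-square formula at 450 and 150, power reaches 99% once the active rate is at least 9.6%, 17.4% or 25.0% for a placebo rate of 1%, 5% or 10%. The statement is plausible, and nothing below depends on it except the remark on the trial's conclusion.

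**2. Number of strata, before pooling.**
- Main test: 38 × 2 × 2 = 152 cells, 600/152 = 3.9 subjects each.
- Sensitivity tests: 38 × 2 = 76 cells, 600/76 = 7.9 subjects each.

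**3. Information kept by the CMH test.** A stratum with n1 active and n0 placebo subjects (n in total) contributes n1·n0/n. The total is compared with the unstratified value, 450 × 150/600 = 112.5. Small cells lose information because a cell holding one arm contributes nothing. For example, a cell of 3 active and 1 placebo gives 0.75 and a cell of 3 active and 0 placebo gives 0. Merged, they give 6 × 1/7 = 0.86.

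Simulated for 600 subjects with permuted blocks within site × toxin history × severity, half severe, 30% or 50% prior users, and equal or variable expected site sizes:

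| Site pooling | Blocks | Three factors | Two factors | Gain (points) |
|---|---|---|---|---|
| None | 4 | 91-92% | 96-97% | about 4-6 |
| None | 8 | 86-87% | 93-94% | about 6-8 |
| Sites under 16 merged | 4 | 96-98% | 99% | about 1-3 |
| Sites under 16 merged | 8 | 93-96% | 97-98% | about 2-4 |

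The mean site size is 600/38 = 15.8, so a threshold of 16 pools many sites. It is one illustration, not the sponsor's rule.

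**4. Effect on the test statistic.** 500 runs per setting, blocks of 4, no pooling, data missing completely at random. Log-odds effects were 0.5 for toxin history and 0.8 for FWS, with site SD 0.3. Complete data stand in for multiple imputation. Mean CMH chi-square:

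| Assumed rates | Missing | Main, 3 factors | NRI, 3 factors | NRI, 2 factors |
|---|---|---|---|---|
| 60% / 2% | 2% | 132.4 | 127.9 | 139.0 |
| 60% / 2% | 5% | 131.9 | 121.1 | 131.1 |
| 60% / 2% | 10% | 131.2 | 110.4 | 118.8 |
| 30% / 5% | 5% | 38.4 | 35.9 | 37.1 |
| 15% / 5% | 5% | 11.3 | 10.6 | 11.1 |

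In the second row, like-for-like strata show an NRI penalty of 131.9 − 121.1 = 10.8. With the protocol's strata the visible penalty is 131.9 − 131.1 = 0.8. At 10% missing the penalty is 131.2 − 110.4 = 20.8, and the strata change returns 118.8 − 110.4 = 8.4 of it.

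**5. Effect on the risk difference.** Changing only the strata moved the average Mantel-Haenszel risk difference by about 0.1 point at most (for example 0.2552 to 0.2541). Within a single simulated trial the mean absolute change was 0.5-0.8 points. For comparison, at 60%/2% and 2%, 5% and 10% missing, NRI alone moved the risk difference by 1.2, 2.9 and 5.7 points, and as-observed alone by 0.4, 0.7 and 1.0 points.

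**6. Effect on significance.** At 60%/2% and 30%/5%, every analysis was significant in all 500 runs of each setting. At 15%/5% with 5% missing, the share significant was 94.4% (main), 92.8% (NRI, same strata) and 94.2% (NRI, reduced strata).

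**The case against.** **The operative text may differ.** Protocol 7.1 leaves full detail to the SAP. SAP version 5.0 (08 April 2023) is later than the protocol synopsis (01 August 2022), and SAP 1.0 says it contains changes to the protocol's analyses. With its strata wording blacked out, nobody outside the sponsor can tell whether the mismatch survives. This stands. The finding concerns the protocol text, and the first step is to look at the unredacted SAP.

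**A reader might infer that the effect of missing data cannot be isolated at all.** The documents do not support that. NRI and as-observed share the same strata, so comparing them with each other varies only the missing-data rule. The summary measures are response rates and rate differences, and SAP 9.3.2 builds the confidence interval from a normal approximation. On the visible wording, the strata govern the test and not necessarily the estimates. The confounding lies in the test results set against the main one.

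**The simulated offset is flattering.** Complete data carry more information than multiple imputation would, and site pooling was left out. Both are fair. The chi-square table shows the mechanism and its direction, not a forecast.

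**Sensitivity analyses may vary more than one thing.** Protocol 7.4 also wants them to characterise the extent of response. That permits a different stratification, but it does not explain one introduced without comment.

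**A reader might also infer that toxin use history must be a subgroup,** because SAP 9.6 lists another randomisation factor ("Baseline FWS at maximum frown (moderate, severe"). That does not follow. Site is a randomisation factor too and is not listed, those summaries are descriptive, and the matter is separate from the strata.

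**Conclusion.** The mismatch is explicit within Protocol 7.4: three factors for the main test, two for the sensitivity tests, with no reason and no bridging analysis. It blurs the comparison of the NRI and as-observed CMH results with the main multiple-imputation result. The extra CMH information is about 4-8 points without site pooling and about 1-4 points with the illustrative pooling, under assumed blocks of 4 or 8 and 30-50% prior users. That can partly offset the NRI penalty on the test statistic. In the unpooled setting with few missing data it can exceed it, though complete data there stood in for multiple imputation.

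A reader might go further and suspect the trial's result. The figures do not support this. The risk difference barely moves, and with stated power above 99% the conclusion is unlikely to change. The harm is to interpretation, and it holds for the current plan only if the blacked-out SAP text has not already aligned the strata.

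**What to change.** - Check the unredacted SAP 9.3.2 and 9.3.3. If they already use common strata, correct Protocol 7.4 or record the difference in the SAP's account of changes.
- Otherwise state that the NRI and as-observed analyses use exactly the strata of the main CMH test (site, toxin use history, baseline FWS) with the same site pooling.
- If toxin use history is left out on purpose, give the reason and add a multiple-imputation CMH test stratified by site and baseline FWS, so that the two changes can be read apart.

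The cost is wording, plus one extra table if the bridging analysis is chosen. It needs no new data, no extra subjects and no change to the primary test.
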